#### 4. STUDY POPULATION

## 4.1 Population (base)

Five patients with FAP will be selected and invited for study participation. These patients must have severe rectal or pouch polyposis for which surgery is expected within a few years. These patients are selected from our large cohort of patients with FAP (n≈200). Selection will not be based on sex and age.

#### 4.2 Inclusion criteria

In order to be eligible to participate in this study, a subject must meet all of the following criteria:

- ≥ 18 years
- -A genetically confirmed APC mutation
- -Classical FAP phenotype (100-1000 colorectal adenomatous polyps)
- -Subtotal colectomy with ileorectal anastomosis (IRA) or total colectomy with ileo-anal pouch anastomosis (IPAA)
- -Severe rectal or pouch polyposis, defined as having >25 polyps amenable to complete removal (InSiGHT 2011 Staging System score of 3, see below)
- -Fertile patients must use effective contraception during study treatment and until 12 weeks after study treatment

InSiGHT 2011 Staging System (InSiGHT Meeting 2011, San Antonio, TX)

Stage	Polyp description
0	0-10 polyps, all <5mm
1	10-25 polyps, most <5mm, none > 1cm
2	10-25 polyps, any >1 cm, amenable to complete removal
3	>25 polyps amenable to complete removal, or any incompletely removed sessile polyp, or any prior evidence of high grade dysplasia, even if completely excised
4	>25 polyps not amenable to complete removal, or any incompletely excised sessile polyp showing high grade dysplasia; any invasive cancer

#### 4.3 Exclusion criteria

A potential subject who meets any of the following criteria will be excluded from participation in this study:

## General exclusion criteria:

Version number: ,date 13 of 40

- -Inability to give informed consent
- -Participation in another interventional clinical trial

#### Medical history:

- -Subjects who are pregnant or breast-feeding, proved with a negative pregnancy test if female of child-bearing potential
- -Prior pelvic irradiation
- -Invasive malignancy in the past 5 years
- -Subjects who are HIV positive
- -Subjects with severe systemic infections, current or within 2 weeks prior to study start
- -Subjects with known severe restrictive or obstructive pulmonary disorders
- -Known sucrase insufficiency, isomaltase insufficiency, fructose intolerance, glucose malabsorption, galactose malabsorption, galactose intolerance or Lapp-lactase deficiency
- -History of pulmonary embolism or deep venous thrombosis
- -Major surgery less than or equal to 2 weeks prior to enrollment or any planned surgery within treatment period
- -Active post-operative complication, e.g. infection, delayed wound healing

#### **Co-medication:**

- -History of hypersensitivity to sirolimus or to drugs of similar chemical classes
- -Regular NSAID use (defined as more than twice a week for 4 consecutive weeks) within 3 months prior to baseline
- -Use of other FAP directed drug therapies (accepted if discontinued 3 months prior to start of the study)
- -Subjects requiring systemic anticoagulation
- -Co-medication that could interact with sirolimus

#### Lab results:

- -Abnormal laboratory results (assessed within 14 days prior to start of study drug):
  - -Significant abnormalities in hepatic function

-ALAT, ASAT, GGT, AF, LDH: > 1.5 times ULN

-Significant hematologic abnormalities

-Hb: <7.0 mmol/L

-Thrombocytes: <100 10E9/L

-Leukocytes: <4.0 10E9/L

-Increased fasting serum cholesterol or triglyceride (whether or not on lipid-lowering therapy)

-Serum cholesterol: >7.8 mmol/L

-Serum triglycerides: >4.5 mmol/L

-Increased glucose (venous, fasting): >6.4 mmol/L

-Electrolyte abnormalities

-Total serum calcium (corrected for albumin): <2.0 mmol/L

-Potassium: <3.0 mmol/L

-Phosphate: <1.3 mmol/L

-Calculated glomerular filtration rate (GFR) less than 40 mL/min/1.73m2 using the simplified Modification of Diet in Renal Disease (MDRD) formula

-Urine specimen:

-Spot urine protein to creatinine ratio (UPr/Cr) greater than or equal to 0.5

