As described in chapter 6.2, a significant polyp reducing effect of sirolimus is to be expected. The patients that will be included, are likely to undergo a subtotal colectomy with ileoanal pouch anastomosis or an end ileostomy on a short term base due to the severity of polyposis. These invasive types of surgery are accompanied with a significant risk of comorbidities (29). Even after surgery, patients will develop polyps in the remaining intestinal tissue and therefore surveillance sigmoidoscopies are needed to prevent the development of cancer (5, 30-32). There is currently no alternative treatment available for these patients. Therefore, a medical treatment to postpone or even prevent surgery could be beneficial. If a polyp reducing effect is shown, this therapy could possibly also be beneficial in postponing a preventive colectomy in patients with FAP who have their colon in situ and in postponing a duodenectomy in patients with severe duodenal polyposis.

Version number: ,date 18 of 40

Table 1. Side-effects of sirolimus (SPC)

System/organ	Very frequent	Frequent	Less frequent	Seldom
	(≥1/10)	(≥1/100 to <1/10)	(≥1/1000 to <1/100)	(≥1/10.000 to <
Infections	Pneumonia Fungal infection Viral infection Bacterial infection Herpes simplex infection Urinary tract infection	Sepsis Pyelonephritis CMV infection Herpes zoster infection	Clostridium difficile colitis Mycobacterial infection (incuding tuberculosis) EBV viral infection	
Neoplasms, benign, malignant and non-specified (including cysts and polyps)		Skin cancer	Lymphoma/ post- transplantation lymphoproliferative conditions	
Blood and lymphatic disorders	Thrombocytopenia Anemia Leukopenia	Hemolytic-uremic syndrome Neutropenia	Pancytopenia Thrombotic thrombocytopenic purpura	
Hepatic and biliary disorders			Hepatic failure	
Immune system disorders		Hypersensitivity disorders such as anaphylactic/anaphylactoid reactions, angio-edema		
Feeding and metabolic disorders	Hypokalemia Hypophosphatemia Hyperlipidemia (such as Hypercholesterolemia) Hyperglycemia Hypertriglyceridemia Diabetes mellitus			
Nervous system disorders*	Headache			
Cardiac disorders	Tachycardia	Pericard effusion		
Vascular disorders	Lymphocele Hypertension	Venous thrombosis (such as deep venous thrombosis)	Lymphedema	
Respiratory, chest and mediastinal disorders		Pulmonary embolism Pneumonitis Pleural effusion Epistaxis	Pulmonary hemorrhage	Alveolar protein

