#### 7.3.1 Specific criteria for withdrawal

Participants will be withdrawn from treatment under the following circumstances:
-If any of the exclusion criteria apply during the study

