#### 11.2 Synthesis

To reduce the risk of side-effects related to sirolimus, a relatively low trough level will be managed. Furthermore, regular telephonic contact, trough level testing, laboratory testing and physical examination will lead to an early detection of any side-effects. We believe this could help patients, who would otherwise need surgery on a short term. As of today no strict contraindications exist for the use sirolimus. However, we exclude patients using medications that could interact with sirolimus. Furthermore, patients with specific laboratory abnormalities as well as patients with specific conditions (such as a deep venous thrombosis or sucrose insufficiency) that could deteriorate due to the use of sirolimus or that could influence the effect of sirolimus are excluded.

We will use tattoos with SPOT™ for marking the polyp sites, which has been used for many years in colonoscopy practice (26). No side-effects of SPOT have been described in the literature. Furthermore, colonic biopsies are accompanied by a minimal risk of perforation, bleeding and infection. These complications have been described in some case reports after hot biopsy but mostly in patients with pre-existent ulcerative colitis or infectious colitis. Bleeding after hot biopsy has been reported to occur in up to 0.26% and perforation in up to 0.01% after hot biopsy. During our study only cold biopsies will be obtained. Only case reports have reported on complications after cold biopsy (27, 28). These complications are cited in the written patient information.

Version number: ,date 37 of 40

In our opinion, treatment with sirolimus could help patients, who would otherwise need surgery on a short term base associated with a significant risk of morbidity and mortality. By applying the above risk management, we believe this treatment is justified. Results of this pilot study could help in creating a future trial assessing the effect of sirolimus in patients with FAP.

Version number: ,date 38 of 40

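### The phosphate limit in 4.3 (<1.3 mmol/L) is labelled an abnormality but lies inside every adult range assumed here, and 7.3.1 can be read as reusing it on treatment

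*Combined protocol and SAP*

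**What the plan says.** Section 4.3 of the protocol (laboratory part) opens with "Abnormal laboratory results (assessed within 14 days prior to start of study drug". Its short group of electrolyte limits has three entries: "Total serum calcium (corrected for albumin): <2.0 mmol/L", "Potassium: <3.0 mmol/L" and "Phosphate: <1.3 mmol/L". No phosphate reference range is given anywhere, and no reason is given for 1.3.

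The only rationale for the laboratory exclusions is general. Section 11.2 says the trial leaves out "patients with specific laboratory abnormalities as well as patients with specific conditions" that might worsen on sirolimus or alter its effect. Table 1 in section 6.4 puts "Hypokalemia Hypophosphatemia Hyperlipidemia" together in the column for side-effects seen in at least 1 in 10 patients.

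On the pool, section 4.1 says "These patients are selected from our large cohort of patients with FAP", about 200 people, but only those with severe rectal or pouch polyposis qualify. Five are to be enrolled.

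Section 7.3.1 withdraws participants from treatment "If any of the exclusion criteria apply during the study". Section 7.2 has phosphate measured at baseline and every three months. Section 7.4 says withdrawn participants are not replaced.

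**The concern.** The list is meant to screen out abnormal values. A limit inside the normal range does something else: it turns away people whose phosphate is normal. Here those people are drawn from the subset of one centre's cohort with severe polyposis, and they must also pass many other criteria. Every needless screen failure makes it harder to find five participants and gives nothing in return that the protocol describes.

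A second question follows from 7.3.1. If the exclusion criteria carry over to the treatment period, a phosphate of, say, 1.2 at month 3 would end treatment, even where the laboratory calls that value normal. Sirolimus is listed as very frequently lowering phosphate, so drift below the limit is foreseeable. With five participants and no replacement, each withdrawal matters.

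**Working it through.** The protocol states no reference range and no expected screen-failure rate, so it has no figure to reproduce. The check asks what share of healthy adults falls below 1.3 under a spread of plausible ranges.

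**Inputs.** The limits 1.3 (phosphate), 3.0 (potassium) and 2.0 (calcium) come from 4.3. All reference ranges below are assumptions. So is the use of a healthy-adult distribution for patients who have had a colectomy for FAP.

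**Model.** Each range is taken as the central 95% of a normal distribution: mean = midpoint, SD = width / 3.92.
- Share excluded: p = Φ((1.3 − mean) / SD).
- By construction 2.5% lie below the lower limit, so the share of those excluded who are in range is (p − 0.025) / p.

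**Worked example, 0.8-1.4.** Mean = 1.1 and SD = 0.6 / 3.92 = 0.153. Then (1.3 − 1.1) / 0.153 = 1.31, so p = 0.904. In-range share = (0.904 − 0.025) / 0.904 = 0.972.

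| Assumed range (mmol/L) | Below 1.3 | Of those, in range |
|---|---|---|
| 0.8-1.4 | 90.4% | 97.2% |
| 0.87-1.45 | 82.8% | 97.0% |
| 0.8-1.5 | 80.0% | 96.9% |
| 0.9-1.5 | 74.3% | 96.6% |
| 0.9-1.6 | 61.0% | 95.9% |
| 1.0-1.6 | 50.0% | 95.0% |
| 1.1-1.7 | 25.7% | 90.3% |

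**Sensitivity to the distribution.** A lognormal model for the two end ranges gives 32% and 93% instead of 26% and 90%.

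**Where the point would fail.** For a range of 1.3-1.9, mean = 1.6 and SD = 0.153, so (1.3 − 1.6) / 0.153 = −1.96 and p = 0.025. The limit would then be an ordinary lower reference limit. In the other direction, a range of 0.6-1.3 gives p = 0.975.

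**Neighbouring limits, same model.**
- Potassium <3.0 excludes 0.05% (range 3.5-5.0) to 0.7% (range 3.2-4.8).
- Calcium <2.0 excludes 0.004% (range 2.20-2.60) to 0.9% (range 2.05-2.55).

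Both stay under 1% throughout.

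**The withdrawal rule.** Two texts must be read together. Section 7.3.1 refers to any exclusion criterion and makes no exception for laboratory limits. Section 4.3 attaches a 14-day pre-treatment window to the laboratory limits. On the first text alone, a month-3 phosphate below 1.3 ends treatment. On the second, a month-3 value cannot meet the criterion at all. The protocol does not say which governs.

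I have not converted the shares into numbers to be screened. The size of the eligible pool and the failure rate on the other criteria are not stated.

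**The case against.** The strongest objection is that the premise is not in the documents. No range is given, every range in the table contains 1.3, and the span from a quarter to nine-tenths is wide. That stands: the size is uncertain, and the conclusion is conditional on the local lower limit being below about 1.3. The direction, however, does not depend on any one range in the table.

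A second objection is that a high floor may be deliberate caution, since hypophosphatemia is listed as very frequent, and 11.2 also covers abnormalities that could influence the drug's effect. This is possible. But 11.2 speaks of abnormalities, which does not explain a floor inside normal. Hypokalemia sits in the same frequency class, and potassium has no comparable floor. It is true that no other limit in the list has its own justification. The others, though, do not appear to contradict their heading.

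Third, the 14-day window in 4.3 may confine the laboratory limits to screening. Section 7.3.1 still has clear content without them, such as pregnancy, severe infection or interacting co-medication. Month 3 is also the only scheduled on-treatment laboratory visit before the final one. The safety committee (8.5) decides measures for adverse events, and participants withdrawn after at least one month still have a sigmoidoscopy (7.5). All of this stands, and it makes the 7.3.1 point an ambiguity and a secondary one.

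A reader might infer three stronger things. One is that 1.3 is a typing or unit error; the documents cannot settle that. Another is that the limit biases the results; it acts before treatment in a single-arm descriptive pilot, and nothing shows it distorting the change in polyp size. The third is that the protocol orders withdrawal for a normal phosphate; that is only one reading.

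**Conclusion.** The point holds conditionally. Unless the laboratory's lower limit for phosphate is about 1.3 mmol/L or higher, the entry rule does not isolate abnormal values. It would exclude roughly a quarter to nine-tenths of healthy adults, almost all of them in range, and so is out of line with the calcium and potassium limits beside it. The consequence is avoidable screen failure in a restricted pool of unstated size. No harm to participants from a stricter floor is shown.

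The percentages rest on assumed ranges, a normal model and a healthy-adult distribution. The 7.3.1 wording adds an ambiguity that could cost a non-replaced participant their treatment, and it should be closed. Severity is minor to moderate, with moderate confidence.

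**What to change.** 1. Check the figure 1.3 and its unit against the local laboratory's phosphate range.
2. In 4.3, replace it with that laboratory's lower reference limit, or a lower value. By construction, a limit set at the lower reference limit excludes about 2.5% of healthy adults, and truly low phosphate is still excluded. Adding a justification for 1.3 would explain the rule but would not remove the needless exclusions.
3. In 7.3.1, add one sentence: the laboratory limits of 4.3 apply at screening only, and on-treatment laboratory abnormalities go to the safety committee.

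The cost is a short amendment to two sections. No test or visit is added, because phosphate is already measured at baseline and at the three-monthly visits.

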#### 4.4 Sample size calculation

As this is a pilot study that has not been performed in humans previously, no sample size calculation is being done. We believe a number of 5 patients is sufficient for the explorative purpose of our study.

Version number: ,date 15 of 40

#### 5. TREATMENT OF SUBJECTS

#### 5.1 Investigational product/treatment

Participants will be given sirolimus tablets. The starting dose is 2 mg once daily which will be given in 1mg tablets. On day 7 the first trough level is measured (using the LC-MS/MS method) and if not within the target range of 5-8ng/ml, dosing adjustments are made. In case of dosing adjustments, the next trough level is measured seven days later and this is repeated weekly until the target range is achieved. In case trough levels are within the target range, the next trough level measurement is at month 3, after which dosing adjustments are made if necessary, and at month 6. The maximum daily dose is 40mg. No placebo is given.

We estimate that a total number of 2000 tablets of 1mg are needed: 2 tablets a day for 6 months for 5 patients resulting in approximately 1800 tablets, plus 200 additional tablets in case of loss or if dosing adjustments are needed.

#### 5.2 Use of co-intervention

Female participants who are sexually active must use adequate contraception as confirmed by three monthly pregnancy tests and male patients need to use adequate contraception as well. Adequate contraception needs to be continued until 12 weeks after therapy. Furthermore, any new concurrent medication that is started during the study needs to be reported. If known to have an interaction with sirolimus, an additional trough level measurement needs to be done. Patients will visit the AMC at baseline, month 3 and month 6 for the interventions as mentioned in chapter 1 'Study design' (physical examinations, laboratory tests, pregnancy test, urine specimen , questionnaires) and weekly for sirolimus trough level testing until the target range has been achieved. Moreover, monthly telephone check-ups will be performed.

Endoscopies that take place at baseline and at 6 months follow-up are not considered cointerventions, as these are performed in a frequency that is consistent with our practice guidelines. Tattoos that are placed during these procedures are considered additional interventions and biopsies that are done can partly be considered as additional interventions, as some of these would have been done in routine care: 5 biopsies of normal mucosa are additional, 5 biopsies of adenomatous tissue are part of routine care.

## 5.3 Escape medication

In case of pain due to any cause, the use of paracetamol is recommended instead of NSAIDS.

Version number: ,date 16 of 40

#### 6. INVESTIGATIONAL PRODUCT

#### 6.1 Name and description of investigational product

The investigational product is sirolimus. Please see the SPC text of sirolimus for further information.

## 6.2 Summary of findings from non-clinical studies

Please see the SPC text of sirolimus. The text is based on an indication (immunotherapy in patients who received a renal transplantation) that is different than the indication we will investigate. This drug has not yet been tested in patients with FAP. Our hypothesis of the polyp reducing effect of sirolimus is based on mouse model studies. As described in the introduction, recently it was shown that the mTOR inhibitor sirolimus can cause tumour cells to undergo growth arrest and differentiation in APC-deficient mice (14). Signalling through the mTOR pathway is necessary for epithelial cell proliferation and tumour growth (15, 16). It was shown that mTOR complex 1 (mTORC1) activity is required for the proliferation of APC-deficient enterocytes. This complex mediates inhibition of eEF2 kinase, which is needed for the proliferation of APC-deficient cells. Sirolimus targets eEF2 resulting in growth arrest and differentiation of tumour cells. The effect of sirolimus on colonic adenoma regression was confirmed in other mice studies, with one of them showing beneficial effects in the small bowel (17-22). Sirolimus seems to inhibit polyp formation and could even lead to regression of polyps (21, 23). Moreover, it seems to increase survival and time to progression to dysplasia (20, 21).

#### 6.3 Summary of findings from clinical studies

Please see the SPC text of sirolimus. This drug has not yet been tested in patients with FAP. Therefore findings from clinical human studies investigating the effect of sirolimus for our hypothesized indication cannot be reported. Since February 2014 an American center has been recruiting 15 participants for a pilot study aiming to investigate if mTor pathway activation decreases in patients with surgically-resectable desmoid tumors which are removed following pre-operative treatment with sirolimus. That study is being conducted in children and young adults (up to 29 years), which includes patients with FAP. Results are expected in 2016 (25).

#### 6.4 Summary of known and potential risks and benefits

Please see the SPC text of sirolimus. Some of the most frequently (>10%) occurring side-effects are thrombocytopenia and anemia, hypertension, electrolyte disorders, urinary tract infections,

Version number: ,date 17 of 40

hypercholesterolemia, hyperglycemia and abdominal pain. Some of the less frequent, but more severe side-effects are sepsis, deep venous thrombosis and skin cancer and self-limiting oral stomatitis. All known side-effects can be found in the Table 1. The incidence of several of these side-effects can increase by an increasing trough level of sirolimus. By applying a relatively low dosing range and frequent trough level testing, we believe these risks have been minimized in our study.

Side-effects of sirolimus as reported in the SPC text apply to patients with a renal transplantation. Most of these side-effects were reported in patients who used sirolimus in combination with other immunosuppressive drugs. We exclude patients who use other immunosuppressive therapy. Moreover, compared to patients with FAP, patients with a renal transplantation more frequently have (severe) comorbidities and additionally, sirolimus will be given for a short amount of time (6 months). Therefore, side-effects of sirolimus might be less frequently found in our participants.

We will use tattoos with SPOT™ for marking the polyp sites, which has been used for many years in colonoscopy practice (26). No side-effects of SPOT have been described in literature. Furthermore, colonic biopsies are accompanied by a minimal risk of perforation, bleeding and infection. These complications have been described in some case reports after hot biopsy but mostly in patients with pre-existent ulcerative colitis or infectious colitis. Bleeding after hot biopsy has been reported to occur in up to 0.26% and perforation in up to 0.01% after hot biopsy. During our study only cold biopsies will be obtained. Only case reports have reported on complications after cold biopsy (27, 28). These potential complications are cited in the written patient information.

As described in chapter 6.2, a significant polyp reducing effect of sirolimus is to be expected. The patients that will be included, are likely to undergo a subtotal colectomy with ileoanal pouch anastomosis or an end ileostomy on a short term base due to the severity of polyposis. These invasive types of surgery are accompanied with a significant risk of comorbidities (29). Even after surgery, patients will develop polyps in the remaining intestinal tissue and therefore surveillance sigmoidoscopies are needed to prevent the development of cancer (5, 30-32). There is currently no alternative treatment available for these patients. Therefore, a medical treatment to postpone or even prevent surgery could be beneficial. If a polyp reducing effect is shown, this therapy could possibly also be beneficial in postponing a preventive colectomy in patients with FAP who have their colon in situ and in postponing a duodenectomy in patients with severe duodenal polyposis.

Version number: ,date 18 of 40

Table 1. Side-effects of sirolimus (SPC)

System/organ	Very frequent	Frequent	Less frequent	Seldom
	(≥1/10)	(≥1/100 to <1/10)	(≥1/1000 to <1/100)	(≥1/10.000 to <
Infections	Pneumonia Fungal infection Viral infection Bacterial infection Herpes simplex infection Urinary tract infection	Sepsis Pyelonephritis CMV infection Herpes zoster infection	Clostridium difficile colitis Mycobacterial infection (incuding tuberculosis) EBV viral infection	
Neoplasms, benign, malignant and non-specified (including cysts and polyps)		Skin cancer	Lymphoma/ post- transplantation lymphoproliferative conditions	
Blood and lymphatic disorders	Thrombocytopenia Anemia Leukopenia	Hemolytic-uremic syndrome Neutropenia	Pancytopenia Thrombotic thrombocytopenic purpura	
Hepatic and biliary disorders			Hepatic failure	
Immune system disorders		Hypersensitivity disorders such as anaphylactic/anaphylactoid reactions, angio-edema		
Feeding and metabolic disorders	Hypokalemia Hypophosphatemia Hyperlipidemia (such as Hypercholesterolemia) Hyperglycemia Hypertriglyceridemia Diabetes mellitus			
Nervous system disorders*	Headache			
Cardiac disorders	Tachycardia	Pericard effusion		
Vascular disorders	Lymphocele Hypertension	Venous thrombosis (such as deep venous thrombosis)	Lymphedema	
Respiratory, chest and mediastinal disorders		Pulmonary embolism Pneumonitis Pleural effusion Epistaxis	Pulmonary hemorrhage	Alveolar protein
Gastrointestinal disorders	Abdominal pain Diarrhea Constipation Nausea	Pancreatitis Stomatitis Ascites		
Cutaneous and subcutaneous disorders	Rash Acne		Expholiative dermatitis	Hypersensitive
Musculoskelatal and connective tissue disorders	Arthralgia	Osteonecrosis		
Renal and urinary system disorders	Proteinuria		Nephrotic syndrome Focal segmental glomerulosclerosis	

Version number: ,date 19 of 40

System/organ	Very frequent (≥1/10)	Frequent (≥1/100 to <1/10)	Less frequent (≥1/1000 to <1/100)	Seldom (≥1/10.000 to
Reproductive system disorders and breast disorders	Menstruation disorders (including amenorrhea, menorrhagia	Ovarial cysts		
General disrders and disorders at administration site	Edema Peripheral edema Pyrexia Pain Disturbed wound healing	Disturbed wound healing Edema		
Laboratory testing disorders	Increased LDH Increased creatinin Increased liver function tests (such as increased ASAT and ALAT)			

\* Side-effect of unknown frequency: posterior reversible encephalopathy syndrome

